***Drugs that may increase tacrolimus blood concentrations**

Calcium Channel Blockers	Antifungal Agents	Macrolide Antibiotics	Gastrointestinal Prokinetic Agents	Other Drugs
diltiazem	clotrimazole	clarithromycin	cisapride	bromocriptine
nicardipine	fluconazole	erythromycin	metoclopramide	chloramphenicol
nifedipine	itraconazole	troleandomycin		cimetidine
verapamil	ketoconazole** voriconazole			cyclosporine danazol ethinyl estradiol methylprednisolone lansoprazole*** omeprazole protease inhibitors nefazodone magnesium-aluminum hydroxide

**In a study of 6 normal volunteers, a significant increase in Tac oral bioavailability ($14\pm5\%$ vs. $30\pm8\%$) was observed with concomitant ketoconazole administration (200 mg). The apparent oral clearance of Tac during ketoconazole administration was significantly decreased compared to Tac alone (0.430 ± 0.129 L/hr/kg vs. 0.148 ± 0.043 L/hr/kg). Overall, IV clearance of Tac was not significantly changed by ketoconazole co-administration, although it was highly variable between patients.

*** Lansoprazole (CYP2C19, CYP3A4 substrate) may potentially inhibit CYP3A4-mediated metabolism of Tac and thereby substantially increase Tac whole blood concentrations, especially in transplant patients who are intermediate or poor CYP2C19 metabolizers, as compared to those patients who are efficient CYP2C19 metabolizers.

***Drugs that may decrease tacrolimus blood concentrations**

Anticonvulsants	Antimicrobials	Herbal Preparations	Other Drugs
carbamazepine phenobarbital phenytoin	rifabutin caspofungin rifampin	St. John's Wort	sirolimus

* This table is not all inclusive.

St. John's Wort (*Hypericum perforatum*) induces CYP3A4 and P-glycoprotein. Since Tac is a substrate for CYP3A4, there is the potential that the use of St. John's Wort in patients receiving Tac could result in reduced Tac levels.

In a single-dose crossover study in healthy volunteers, co-administration of Tac and magnesium-aluminum hydroxide resulted in a 21% increase in the mean Tac AUC and a 10% decrease in the mean Tac Cmax relative to Tac administration alone.

In a study of 6 normal volunteers, a significant decrease in Tac oral bioavailability ($14\pm6\%$ vs. $7\pm3\%$) was observed with concomitant rifampin administration (600 mg). In addition, there was a significant increase in Tac clearance (0.036 ± 0.008 L/hr/kg vs. 0.053 ± 0.010 L/hr/kg) with concomitant rifampin administration.

Interaction studies with drugs used in HIV therapy have not been conducted. However, care should be exercised when drugs that are nephrotoxic (e.g., ganciclovir) or that are metabolized by CYP3A (e.g., nelfinavir, ritonavir) are administered concomitantly with Tac. Similarly, care should be exercised when HCV protease inhibitors (e.g., boceprevir and telaprevir), also metabolized by CYP3A, are administered concomitantly with Tac.

Tac may affect the PK of other drugs (e.g., phenytoin) and increase their concentration. Grapefruit juice affects CYP3A-mediated metabolism and should be avoided.

Other Drug Interactions

Immunosuppressants may affect vaccination. Therefore, during treatment with Tac, vaccination may be less effective. The use of live vaccines should be avoided; live vaccines may include, but are not limited to measles, mumps, rubella, oral polio, BCG, yellow fever, and TY 21a typhoid ([Prograf® PI 1994](#))

18 Appendix 6: Blinding and unblinding

Randomization data are kept strictly confidential. Prior to final clinical database lock, unblinding is allowed only for authorized personnel as described in the table below.

Table 18-1 Blinding levels

Role	Time or Event						
	1	2	3	4	5	6	7
Drug Supply	UI	UI	UI	UI	UI	UI	UI
Randomization Office	UI	UI	UI	UI	UI	UI	UI
Subject	B	B	UI	UI	UI	UI	UI
Treating Physician	B	B	UI	UI	UI	UI	UI
Primary Investigator	B	B	UI	UI	UI	UI	UI
Study Monitor	B	B	UI	UI	UI	UI	UI
Clinical Trial Leader	B	B	B	UI	UI	UI	UI
Data Manager	B	B	UI	UI	UI	UI	UI
PK Bioanalytics	B	UI	UI	UI	UI	UI	UI
PK Expert	B	B	B	UI	UI	UI	UI
Statistician	B	B	B	UI	UI	UI	UI
Translational Medicine Expert	B	B	B	UI	UI	UI	UI
Modeler	B	B	B	UI	UI	UI	UI
Programmer	B	B	B	UI	UI	UI	UI
Data Monitoring Committee	B	B	B	UI	UI	UI	UI

UG Allowed to be unblinded on treatment group level

UI Allowed to be unblinded on individual patient level

B Remains blinded

- 1 Generation of randomization list, QC and lock randomization list
- 2 Patient allocation to treatment
- 3 Treatment administration
- 4 Safety emergency event (unblinding of a single subject)
- 5 Interim analysis (all patients included in the analysis have completed the study)
- 6 Interim analysis (some patients included in the analysis have not yet completed the study)
- 7 Database lock

19 Appendix 7: Clinically notable laboratory values

Laboratory variable	Standard units	SI units
Liver function and related variables		
SGOT (ASAT)	$\geq 3 \times$ ULN	$\geq 3 \times$ ULN
SGPT (ALAT)	$\geq 3 \times$ ULN	$\geq 3 \times$ ULN
Bilirubin	$\geq 3 \times$ ULN	$\geq 3 \times$ ULN
Renal function, metabolic and electrolyte variables		
Urea	$\geq 5 \times$ ULN	$\geq 5 \times$ ULN
Creatinine	After Wk4: ≥ 3 mg/dL OR $>30\%$ above value from preceding visit	After Wk4: ≥ 265 μ mol/L OR $>30\%$ above value from preceding visit
Uric acid	M ≥ 12 mg/dL F ≥ 9 mg/dL	M ≥ 714 μ mol/L F ≥ 535 μ mol/L
Glucose	<45 mg/dL >250 mg/dL	<2.5 mmol/L >13.9 mmol/L
Cholesterol	≥ 350 mg/dL	≥ 9.1 mmol/L
Triglycerides	≥ 750 mg/dL	≥ 8.5 mmol/L
CK (MB)	None	None
Potassium	≤ 3.0 mEq/L ≥ 6.0 mEq/L	≤ 3 mmol/L ≥ 6 mmol/L
Calcium	≤ 6 mg/dL ≥ 13 mg/dL	≤ 1.5 mmol/L ≥ 3.2 mmol/L
Hematology variables		
Hemoglobin	<7 g/dL	<4.39 mmol/L
Platelets (thrombocytes)	<50 k/mm ³ ≥ 700 k/mm ³	$<50 \times 10^9$ /L $\geq 700 \times 10^9$ /L
Leukocytes (WBCs)	≤ 2.0 k/mm ³ ≥ 16 k/mm ³	$\leq 2.0 \times 10^9$ /L $\geq 16 \times 10^9$ /L
Hematology variables: differential		
Granulocytes (poly, neutrophils)	$\leq 1,000/\text{mm}^3$	$\leq 1 \times 10^9$ /L
Eosinophils	$\geq 12\%$	$\geq 12\%$
Lymphocytes	$\leq 1,000/\text{mm}^3$	$\leq 1 \times 10^9$ /L
Vital sign variables		
Systolic BP (mm/Hg)	outside of $90 \leq$ SBP ≥ 200 mm/Hg	
Diastolic BP (mm/Hg)	outside $50 \leq$ DBP ≥ 120 mm/Hg	
Notable criteria		

20 Appendix 8: Banff '09 Meeting Report: Antibody Mediated Graft Deterioration and Implementation of Banff Working Groups ¹

- Normal
- Antibody-mediated rejection – due to circulating anti-donor antibodies, C4d, and allograft pathology:
 - C4d deposition without morphologic evidence of acute rejection – C4d, anti-donor antibodies, no signs of acute or chronic rejection, no ATN-like minimal inflammation.
 - Acute antibody-mediated rejection – C4d, anti-donor antibodies, and acute tissue injury, such as: (“suspicious for” if antibody not demonstrated)
 - Type I – ATN-like minimal inflammation
 - Type II – Capillary involvement and/or thromboses
 - Type III – Arterial changes
 - Chronic antibody-mediated rejection – evidence of chronic tissue such as glomerular double contours, peritubular capillary basement membrane multilayering, interstitial fibrosis/tubular atrophy (IFTA), or fibrous intimal thickening in arteries. Borderline changes “suspicious” for acute T cell-mediated cellular rejection. No intimal arteritis present, but there are foci of mild tubulitis with mild interstitial infiltration. Threshold for rejection diagnosis is not met.
 - T cell mediated rejection
 - Type IA - Significant interstitial infiltration (> 25% of parenchyma) and foci of moderate tubulitis (> 4 mononuclear cells/tubular cross section or group of 10 tubular cells).
 - Type IB - Significant interstitial infiltration (> 25% of parenchyma) and foci of severe tubulitis (> 10 mononuclear cells/tubular cross section or group of 10 tubular cells).
 - Type IIA - Mild to moderate intimal arteritis
 - Type IIB - Severe intimal arteritis comprising > 25% of the luminal area
 - Type III - Transmural (full vessel wall thickness) arteritis and/or arterial fibrinoid change and necrosis of medial smooth muscle cells (with accompanying lymphocytic inflammation)
 - Interstitial fibrosis and tubular atrophy**
 - Grade I - Mild interstitial fibrosis and tubular atrophy without (a) or with (b) specific changes suggesting chronic rejection
 - Grade II - Moderate interstitial fibrosis and tubular atrophy (a) or (b)
 - Grade E III - Severe interstitial fibrosis and tubular atrophy and tubular loss (a) or (b)

- Other: Changes not considered to be due to rejection (e.g., post-transplant lymphoproliferative disorder, nonspecific changes, acute tubular necrosis, etc.), specifically:
 - Chronic hypertension - Arterial/fibrointimal thickening with reduplication of elastica, usually with small artery and arteriolar hyaline changes.
 - Calcineurin toxicity - Arteriolar hyalinosis with peripheral hyaline nodules and/or progressive increase in the absence of hypertension or diabetes. Tubular cell injury with isometric vacuolization.
 - Chronic obstruction - Marked tubular dilatation. Large Tamm-Horsfall protein casts with extravasation into interstitium, and/or lymphatics.
 - Acute bacterial pyelonephritis - Intratubular and peritubular neutrophils with destruction of the tubular epithelium.
 - Viral infection - Viral inclusions on histology and immunohistology and/or electron microscopy.

*The recommended format of report is a descriptive narrative signet followed by numerical codes (Banff '09) in parentheses. Categorization should in the first instance be based solely on pathologic changes, and then integrated with clinical data as a second step. More than one diagnostic category may be used if appropriate.

**Glomerular and vascular lesions help define type of chronic nephropathy; chronic/recurrent rejection can be diagnosed if typical vascular lesions are seen. Grades I, II and III may include nonspecific vascular and glomerular sclerosis, but severity is graded by tubulointerstitial features.

¹ ([Sis et al 2010](#))

1.1 Scope of document

The RAP documents contain detailed information to aid the production of Statistics & Programming input into the Clinical Study Report (CSR) for trial “CCFZ533X2201” Part 2 only.

The Statistical analysis plan (SAP) describes the implementation of the statistical analysis planned in the protocol.

1.2 Study reference documentation

This SAP has been developed using Clinical Trial Protocol version v02 (incorporating Amendment 02) dated 11 April 2016.

1.3 Study objectives

1.3.1 Primary objective

- To assess the potential for CFZ533 to act as the primary immunosuppressant in a CNI-free regimen with MMF in *de novo* renal transplant patients as assessed by tBPAR at Month 3 post-transplantation.

1.3.2 Secondary objectives

- To assess the safety and tolerability of CFZ533 administered chronically in combination with MMF and CS up to 3 months against a control
- To assess the PK of multiple IV doses of CFZ533 during the 12-month treatment period
- To quantify the magnitude and duration of peripheral blood CD40 occupancy (free CD40 and total CD40 on B cells) during the treatment period following multiple IV doses of CFZ533
- To compare renal function in CFZ533 treatment arms to control at Month 3 post-transplantation as assessed by:
 - Estimated GFR
 - Proportion of patients with eGFR < 60 mL/min/1.73 m²
 - Proportion of patients with negative eGFR slope
- To evaluate the immunogenicity of multiple IV doses of CFZ533 via the quantitative analysis of anti-CFZ533 antibodies
- To quantify the change from baseline and recovery of peripheral blood total soluble CD40 during the treatment period following multiple IV doses of CFZ533.

[figure not shown]
The assessment of safety and tolerability and comparison of renal function will also be assessed at Month 12.

1.4 Study design and treatment

1.4.1 General overview

Study CCFZ533X2201 is a randomized, three-part, 6- or 12-month, sequential, adaptive, controlled, open-label, multicenter, clinical proof-of-concept study to evaluate the efficacy, safety, tolerability, PK and PD of CFZ533 + MMF + CS, with standard exposure (Part 1) or no Tac (Part 2, 3), for initial and maintenance prophylaxis of organ rejection in adult *de novo* renal transplant recipients as compared to standard of care. As illustrated in Figure 1-1, each study part will evaluate a set of CFZ533 doses or treatment regimens in a parallel arm manner.

Figure 1-1 CCFZ533X2201 study design

Study Part 2 will continue the investigation of efficacy, safety, tolerability, PK and PD with the addition of induction therapy and avoidance of Tac. The initial 3 months of Part 2 will serve as the CNI-free, clinical proof-of-concept (PoC), portion of this trial. During the PoC portion of this study, the ability of CFZ533 to assume the role of the primary immunosuppressant in a regimen of CFZ533+MMF and CS will be evaluated.

1.4.2 Part 2 – Arms 2A-2B

Approximately 45 patients who meet the inclusion criteria will be randomized in a 2:1 fashion within 12 hours pre-transplant to receive one of the 2 treatment arms:

1. Arm 2A, n = 30: Basiliximab 20 mg (Days 0, 4) + CFZ533 at 10 mg/kg IV (17 doses) + MMF 1.0 g BID + CS
2. Arm 2B Control/SoC, n = 15: Basiliximab 20 mg (Days 0, 4) + Tac (4-11 ng/mL) + MMF 1.0 g BID + CS

Induction therapy must be started within 2 hours prior to transplantation, or according to local practice.

The first dose of CFZ533 will be administered IV pre-transplant or intra-operatively. Drug administration will begin after randomization and must be completed by the time of unclamping or up to 6 hours prior to the time of unclamping. Subsequent doses of CFZ533 will be administered IV (Arm 2A), over a period of 12 months.

Other study drugs must be started within 24 hours post-transplant. The second dose of basiliximab will be administered on Day 4, or according to local practice.

[figure not shown]
The day of randomization and transplant will be considered to be study Day 1.

Patients will then undergo Study Completion evaluations.

The primary endpoint of Part 2 will be assessed to determine whether the success criteria (safety and tBPAR) have been met when all patients have completed the Month 3 visit. If it is found that the data up to the Month 3 visit is inconclusive, a reevaluation (interim analysis) will occur after the Month 6 visit.

If the stopping rules are not met and the primary endpoint of Part 2 is fulfilled at Month 3, Part 3 (exposure-response profiling) will be initiated following consultation of the DMC. Cumulative efficacy and safety data will be collected on an ongoing basis during the conduct of the study.

Figure 1-2 Part 2 Design

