2.2 Study Part 2: CNI-free Proof-of-Concept

2.2.1 Primary objective

- To assess the potential for CFZ533 to act as the primary immunosuppressant in a CNI-free regimen with MMF in *de novo* renal transplant patients as assessed by tBPAR at Month 3 post-transplantation

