9.4.3 Supportive analyses

Part 2

The tBPAR (or BPAR) rate will be analyzed at 6 months and 12 months post transplantation using the same method as described for the month 3 analysis in [Section 9.4.2](#).

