- Females of reproductive potential taking CellCept® must receive contraceptive counseling and use acceptable contraception (see [Table 14-1](#) for Acceptable Contraception Methods). Patients must use acceptable birth control during entire CellCept® therapy, and for 6 weeks after stopping CellCept®, unless the patient chooses abstinence (she chooses to avoid heterosexual intercourse completely).
- Patients should be aware that CellCept® reduces blood levels of the hormones in the oral contraceptive pill and could theoretically reduce its effectiveness.

Table 14-1 Acceptable Contraception Methods for Females of Reproductive Potential*

Option 1 Methods to Use Alone	
 • Intrauterine device (IUD) • Tubal sterilization • Patient's partner had a vasectomy 		
OR			
Option 2 Choose One Hormonal Method AND One Barrier Method	Hormone Methods choose 1		Barrier Methods choose 1
	Estrogen and Progesterone 
 • Oral contraceptive pill • Transdermal patch • Vaginal ring Progesterone-only 
 • Injection • Implant 	AND	
 • Diaphragm with spermicide • Cervical cap with spermicide • Contraceptive sponge • Male condom • Female condom
OR			
Option 3 Choose One Barrier Method From Each Column (must choose two methods)	Barrier Methods choose 1		Barrier Methods choose 1
	
 • Diaphragm with spermicide • Cervical cap with spermicide • Contraceptive sponge 	AND	
 • Male condom • Female condom

*Females of reproductive potential include girls who have entered puberty and all women who have a uterus and have not passed through menopause.

15 Appendix 3: Stopping rules

Transition rules are based on both efficacy and safety results from Part 2. In Part 2, treatment arms are as follows:

- A: CFZ533 10mg/kg (IV);
- B is Control

Then the rules are as follows:

- If A is terminated for any reason, then STOP the study.

The following rules are for terminating treatment group(s) from Part 2:

For safety:

- Terminate the treatment group if there are two (2) or more patients presenting with PTLD or PML in that group.
- For toxicities, AEs / infections, and causalities, case-by-case review is needed to determine any treatment group(s) should be terminated.

For efficacy (based on the number of patients with tBPAR):

- If no tBPAR for SoC, then any group with tBPAR ≥ 7 will be terminated.

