6.1.3 Statistical model, assumptions and hypotheses

The number of patients with tBPAR is assumed to follow a binomial distribution, i.e.,

$$r_i \sim \text{Binomial}(n_i, \theta_i)$$

where r_i is the number of patients with tBPAR in treatment group i , n_i is the number of patients in treatment group i and θ_i is the probability of tBPAR.

The efficacy analysis for the first 3 months of Part 2 considers whether a CFZ533 treatment arm meets the pre-defined criteria for initiation of Part 3.

The pre-defined success criteria is considered to be a tBPAR rate difference between the CFZ533 arm and the control group of less than 20 percentage points with at least 60% level of proof.

$$\Pr(\theta_{\text{CFZ533}} - \theta_{\text{SoC}} < 0.20 \mid \text{data}) > 60\%$$

The required posterior probabilities will be estimated from simulations of the posterior distributions of $\theta_{\text{CFZ533}} - \theta_{\text{SoC}}$ and compared to the thresholds for the levels of proof.

The prior distributions will be assumed to be a non-informative Beta(1/3, 1/3) for CFZ533 and an informative prior of Beta(1, 13) for SoC. This informative prior corresponds to an approximate mean response rate of 7% with a 95% confidence interval of (0.2%, 24%) and was determined via a meta-analysis of control therapies.

The posterior mean tBPAR rates for each treatment group and for the difference in mean response rates between treatments will be tabulated together with the 95% credible intervals, the number of patients with tBPAR and the posterior probabilities of being above the thresholds, 10%, 15%, 20%, 25%.

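### The SAP's Month 6 re-evaluation of an undefined inconclusive Month 3 result conflicts, for tBPAR at the planned 30/15, with the termination counts in protocol Appendix 3

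*SAP*

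**What the plan says.** Protocol 2.2.1 sets the Part 2 primary objective "as assessed by tBPAR at Month 3 post-transplantation", and SAP 1.3.1 repeats it. SAP 6.1.3 defines success on tBPAR as a CFZ533-minus-control difference of "less than 20 percentage points with at least 60% level of proof", that is, a posterior probability above 60%. Protocol 9.4.3 lists the later time points under supportive analyses: "The tBPAR (or BPAR) rate will be analyzed at 6 months and 12 months post transplantation using the same method as described" for Month 3.

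SAP 1.4.2 adds that if the "data up to the Month 3 visit is inconclusive, a reevaluation (interim analysis) will occur after the Month 6 visit". SAP 6.1.4 refers to a first interim analysis at Month 3 and a second at Month 6. The same part of SAP 1.4.2 ties Part 3 to Month 3, provided no stopping rule has been triggered: "the primary endpoint of Part 2 is fulfilled at Month 3, Part 3 (exposure-response profiling) will be initiated".

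There are two sets of tBPAR stopping limits:

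- Protocol Appendix 3 depends on the control count. It begins "If no tBPAR for SoC, then any group with tBPAR ≥ 7 will be terminated", then gives 8 or more with one control event and 9 or more with more than one. Termination of arm A for any reason stops the study.
- Protocol 5.5.10 and 9.6 stop an arm when the probability that its true tBPAR rate exceeds 20% is above 90%. SAP Table 1-1 tabulates this rule, and at N=30 it stops at 9 events whatever the control count. The SAP does not carry Appendix 3.

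**The concern.** On tBPAR the criterion has only two outcomes, above 60% or not, so it leaves no middle zone to call inconclusive. If the word is read as covering a tBPAR failure, the SAP keeps open a result that Appendix 3 treats as the end of the study. Two plans for the same trial then imply different actions for the same counts.

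The direction of any later change also matters. Cumulative CFZ533 rejections cannot fall between Month 3 and Month 6. With unchanged denominators, a Month 3 failure could become a pass only because more control patients rejected after Month 3. That says nothing new about whether CFZ533 protected the graft in the first three months. The operating characteristics in protocol 9.6 also describe one application of the success criterion, without a second look.

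**Working it through.** **Inputs.** 30 CFZ533 and 15 control patients (protocol 3.1.4, SAP 1.4.2); priors Beta(1/3, 1/3) and Beta(1, 13), margin 0.20 and threshold 60% (protocol 9.4.2, SAP 6.1.3); limits from Appendix 3 and SAP Table 1-1. Appendix 3 names no time point; its limits are applied here to the Month 3 counts.

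**Formulas.** With r CFZ533 and s control events, the posteriors are Beta(1/3 + r, 1/3 + 30 − r) and Beta(1 + s, 13 + 15 − s). The success probability is Pr(θ_CFZ533 − θ_SoC < 0.20) = ∫ f_SoC(x) · F_CFZ533(x + 0.20) dx, computed numerically.

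**Reproducing the stopping rule behind Table 1-1.** Under Beta(1/3, 1/3), Pr(θ > 0.20) at N=30 is 0.812 for 8 events and 0.904 for 9. The limit of 9 is reproduced, and so are the table's other rows.

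**Success criterion against the stopping limits at 30/15.**

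| Control events | Highest passing count | First failing count | Appendix 3 limit | Table 1-1 limit |
|---|---|---|---|---|
| 0 | 6 (0.656) | 7 (0.495) | 7 | 9 |
| 1 | 7 (0.642) | 8 (0.496) | 8 | 9 |
| 2 | 8 (0.633) | 9 (0.498) | 9 | 9 |
| 3 | 9 (0.628) | 10 (0.502) | 9 | 9 |

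The first failing counts for 0, 1 and 2 control events equal the Appendix 3 limits. With 3 control events Appendix 3 is stricter than the criterion: 9 v 3 passes but is terminated. At 30/15, then, no tBPAR failure escapes Appendix 3. Table 1-1 leaves three failing results running: 7 v 0, 8 v 0 and 8 v 1.

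**How such a result could turn.** With no new CFZ533 event, 7 v 0 passes after one more control rejection (7 v 1, 0.642), 8 v 1 after one more (8 v 2, 0.633), and 8 v 0 after two more (8 v 2).

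**Sensitivity to numbers.** Protocol 3.1.4 and SAP 1.4.2 give approximate numbers. At 28/14, the results 6 v 0, 7 v 1 and 8 v 2 fail the criterion without reaching Appendix 3; at 29/15, 8 v 2 does. No gap appeared at the larger sizes tried, 31/15 to 33/17.

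**Size if Month 6 could overturn Month 3.** Let p be the true Month 3 rates and q the risks of a first tBPAR in Months 3-6 among patients still event-free. The documents do not give q, so q is assumed. Added probability = Σ Bin(r; 30, p_C) · Bin(s; 15, p_S) · Pr(r+i v s+j passes), over Month 3 failures with r ≤ 8, where i ~ Bin(30−r, q_C) and j ~ Bin(15−s, q_S).

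| p_C v p_S | Fails, 8 or fewer events | Added, q 5% v 3% | Added, q 5% v 5% | Added, q 2% v 7% |
|---|---|---|---|---|
| 25% v 4% | 23.0% | 2.3 points | 4.0 | 9.0 |
| 25% v 7% | 17.0% | 1.8 | 3.1 | 6.9 |
| 30% v 4% | 19.8% | 1.9 | 3.3 | 7.5 |
| 30% v 7% | 14.9% | 1.5 | 2.6 | 5.9 |

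The range is about 1.5 to 9 points, or 1.3 to 8.3 if the 9/30 limit is also applied at Month 6. If Appendix 3 is applied at Month 3, the failing set is empty at 30/15 and the addition is zero.

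**The case against.** A reader might infer that the SAP gives a failed Month 3 result a second route to proof of concept. The documents do not say so. SAP 1.4.2 opens Part 3 only on fulfilment at Month 3, SAP 6.1.3 ties the criterion to the first three months, and nothing states that a Month 6 result replaces a Month 3 failure. The Part 3 gate may itself be legacy text: the SAP was written against protocol v02 and describes three parts, while the current protocol describes two. This objection stands, so the point is an ambiguity plus a conflict of counts, not a demonstrated second chance.

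Inconclusive may also refer to safety. Both documents describe the success criteria as safety and tBPAR, and safety has no numeric cut. A safety re-look would not engage the tBPAR limits. This also stands.

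A reader might further infer that no rule for the Month 6 look exists, or that the stopping conflict is simply SAP against protocol. Text is redacted directly after the matching sentence in protocol 3.1.4 and beside the criterion in 9.4.2, so only the visible text can be judged. The 90%/20% rule is the protocol's own, so the conflict with Appendix 3 lies partly inside the protocol.

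Finally, the two harms are alternatives: if Appendix 3 is followed, the added probability is zero at 30/15. The upper end of the range also needs late rejection to be rarer on CFZ533 than on control. None of this defines the term or reconciles the limits.

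**Conclusion.** The point holds in limited form. Applied to tBPAR at 30/15, the Month 6 re-evaluation has no result to act on if Appendix 3 is followed, and three results to act on (7 v 0, 8 v 0, 8 v 1) if only the 90%/20% rule is followed. The match with Appendix 3 is specific to the planned size and breaks at 28/14 and 29/15.

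The possible effect on declaring proof of concept runs from zero (Appendix 3 applied) to about 1.5 to 9 points (9/30 limit only). The latter assumes true Month 3 rates of 25-30% v 4-7%, Month 3-6 risks of 2-5% on CFZ533 and 3-7% on control, unchanged denominators, and a Month 6 look that is allowed to replace Month 3, which the SAP does not state.

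**What to change.** In SAP 1.4.2, state that the tBPAR criterion for proof of concept is judged on Month 3 data only, and that Month 6 and Month 12 tBPAR are supportive, as in protocol 9.4.3, and cannot convert a Month 3 failure. Either limit the Month 6 re-evaluation to safety, and say so, or delete it.

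Reconcile protocol Appendix 3 with protocol 5.5.10 and 9.6 and with SAP Table 1-1, so that one rule covers 7 v 0, 8 v 0 and 8 v 1 and also says what applies when enrolment differs from 30/15. This review does not say which limit is right.

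The cost is a few lines of text. The sponsor gives up an informal second look; Month 6 results are still reported.
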